## 8. STUDY INTERVENTION

### 8.1 Identity of Investigational Products

All participants will receive all vaccines planned by the Swiss vaccinations schedule, the intervention being only a change in the administration scheme (Table 3).

[figure not shown]
[figure not shown]

[figure not shown]
[figure not shown]

[figure not shown]
[figure not shown]

	Age: 6 m	9 m	11-12 m	13 m
Group C.C. (both MMR on Current schd.)	No vaccine	 1 st MMR	 3 rd DTP and PCV  2 nd MMR	No vaccine
Group M.C. (1 st MMR Modified schd., 2 nd MMR Current schd.)	 1 st MMR	No vaccine	 3 rd DTP and PCV  2 nd MMR	No vaccine
Group C.M. (1 st MMR Current schd., 2 nd MMR Modified schd.)	No vaccine	 1 st MMR	 3 rd DTP and PCV	 2 nd MMR
Group M.M. (both MMR on Modified schd.)	 1 st MMR	No vaccine	 3 rd DTP and PCV	 2 nd MMR

Table 3: MMR schedule in the 4 study groups. C: current schedule; DTP: diphtheria-tetanus-pertussis-containing vaccine; m: months of age; M: modified schedule; PCV: pneumococcal conjugate vaccine; schd: schedule. See also Table 2 and Fig 8.

As recommended by the Swiss vaccinations schedule, the dose of the intervention is the following:

 **MMR:** 0.5 ml of MMR vaccine injected intramuscularly in the deltoid region or in the anterolateral area of the thigh.

The following vaccines are expected to be administered by the treating paediatrician at 11-12 months of age, as planned and recommended by the Swiss vaccinations schedule:

 **DTP:** 0.5 ml of a diphtheria, tetanus, pertussis, poliovirus, ± *Haemophilus influenzae* type b ± hepatitis B vaccine injected intramuscularly in the deltoid region or the anterolateral area of the thigh.

 **PCV:** 0.5 ml of pneumococcal conjugate vaccine injected intramuscularly in the deltoid region or the anterolateral area of the thigh.

### **8.1.1 Experimental Intervention**

The interventional product is the measles-mumps-rubella vaccine Priorix from GlaxoSmithKline (see section 3.2). It comes as a powder (that is the lyophilised MMR component) and a solvent for solution for injection in a pre-filled syringe.

The lyophilised measles-mumps-rubella component is a white to slightly pink powder.

The solvent is a clear and colourless solution.

The vaccine must be reconstituted by adding the entire contents of the pre-filled syringe of solvent to the vial containing the powder. The mixture should be well shaken until the powder is completely dissolved in the solvent. Due to minor variation of its pH, the reconstituted vaccine may vary in colour from clear peach to fuchsia pink without deterioration of the vaccine potency.

There will be no deviation from the commercial product and the usual administration mode. The vaccine (0.5 ml) will be injected intramuscularly in the deltoid region or in the anterolateral area of the thigh.

### **8.1.2 Control Intervention (standard/routine/comparator treatment)**

The interventional product given to the control group will be the same as for the intervention group (see section 8.1.1), but with a different schedule of administration (see section 8.1).

### **8.1.3 Packaging, Labelling and Supply (re-supply)**

Not applicable, we will use the same vaccine as used routinely.

### **8.1.4 Storage Conditions**

The MMR vaccines will be stored in their original package in order to protect them from light, and kept in the refrigerator (2°C-8°C). It should not be frozen.

After reconstitution, the vaccine should be injected promptly after reconstitution, or stored at 2°C-8°C and used within 8 hours of reconstitution.

## **8.2 Administration of experimental and control interventions**

### **8.2.1 Experimental Intervention**

See section 8.1 and 8.1.1.

### **8.2.2 Control Intervention**

See section 8.1 and 8.1.2.

## **8.3 Dose modifications**

Not applicable.

## **8.4 Compliance with study intervention**

Not applicable.

## **8.5 Data Collection and Follow-up for withdrawn participants**

As stated in section 7.4, If withdrawal is due to an AE, appropriate follow-up visits or medical care will be arranged, with the agreement of the subject's parent, until the AE has resolved, stabilised or a non-trial related causality has been assigned.

## **8.6 Trial specific preventive measures**

Not applicable.

## **8.7 Concomitant Interventions (treatments)**

Not applicable.

## **8.8 Study Drug Accountability**

Not applicable, we will use the same vaccine as used routinely.

## 8.9 Return or Destruction of Study Drug

Not applicable, we will use the same vaccine as used routinely.

## 9. STUDY ASSESSMENTS

### 9.1 Study flow chart(s) / table of study procedures and assessments

Visit number	V1		V2		V3 a		V4	
Time point	t 0	t 0 to t +3m	t +3m	t +3m to t +6m	t +6m	t +7m	t +6m to t +18m	t +18m
Age of participant	6mo	6mo to 9mo	9mo	9mo to 12mo	12mo	13mo	12mo to 24mo	24mo
Allowed time frame	±2w	±1w	±2w	±1w	±2w	±2w	±1w	±4w
Recruitment								
Screening, eligibility check	X							
Inclusion and randomisation	X							
Baseline questionnaire b	X							
Intervention: MMR vaccination								
- Group C.C.			X		X			
- Group M.C.	X				X			
- Group C.M.			X			X		
- Group M.M.	X					X		
Assessments								
Clinical assessment c	X		X		X			X
Fortnightly questionnaire		X...X...X...X d		X...X...X...X e			X...X...X...X e	
Vaccine diary (S/AE)		X f		X f			X f	
Contact with treating paediatrician	X		X		X			X
Health record check	X		X					X
Blood collection (Part 2 only)	X		X					X

C: current schedule; MMR: measles-mumps-rubella vaccination; M: modified schedule; m: month; mo: month-old; S/AE: (serious) adverse event; V: visit; w: week.

a Timing of V3 differs between groups: 13 mo for Group M.M. and Group C.M., and 12 mo for Group M.C and Group C.C. If funding is insufficient, V3 might be simplified and delegated to the treating paediatrician.

b Includes demographics, medical history.

c Includes physical examination and eczema assessment using SCORAD.

d every 2 weeks.

e every month.

f follow-up 42 days after vaccination.

### 9.2 Assessments of outcomes

#### Clinical outcomes

##### Source of information:

- 1) Online parent questionnaires sent every two weeks for the first 3 months, then monthly.
- 2) Contact with the treating paediatrician at 9 and 24 months for completion of any missing illness data.
- 3) Access to medical records.

The data collected (Table 4) will enable the extraction of the following measurement for each participant for both infectious and allergic episodes: number of episodes between 6 months and 2 years of life, interval between inclusion and first episode, characteristics of each episode (e.g. diagnosis, duration) and treatment (e.g. type, route, duration), complications, hospitalisation (e.g. reason, length of stay, outcomes), number of days free of episode. Episodes of trauma/accidents will be used as control events.

Data collected at inclusion, confirmed with treating paediatrician and hospital records
Demographics: parental age, education, ethnicity, country of birth; household composition, age of siblings; location of home (countryside, urban); socioeconomic group; date of birth*.
Potential confounding and or mediating factors pre-randomisation: maternal pregnancy factors (mode of delivery, infection, antibiotics, probiotics, smoking, supplements, vaccines), infant factors (sex, gestational age, season of birth, sepsis, antibiotics, probiotics, alimentation, supplements and medications); family history of allergic disease (eczema, hay fever, asthma, food and non-food allergies); household smoking; pet exposure.
Data collected with online questionnaires, confirmed with treating paediatrician and hospital records
Infection outcome data: episodes of: upper/lower respiratory tract infection (including croup, pharyngitis, otitis media, bronchiolitis, bronchitis, pneumonia), cold sores/mouth ulcers, gastroenteritis, urinary tract infection, bone-joint infection, other infection.  For all infections: diagnosis, pathogen(s), site of infection, date, symptoms, duration, severity, outcome, health care use, hospital admission (more than 1 day), treatment.
Trauma/accident data (used as control events): medically attended accidents, burns or trauma.  For all occurrences: date, severity, health care use, hospital admission (more than 1 day).
Allergic disease outcome data: presence of eczema, food allergy, wheezing disease.  Eczema - diagnosis using adapted version of the UK diagnostic tool,  parent-reported doctor-diagnosed, and clinical evaluation during study visits; symptoms; severity and impact on quality of life using the POEM  and the SCORAD  scores.  Food-allergy – parent-reported doctor-diagnosed food allergy or sensitisation; diagnostic test used: participants with suspicion of food allergy will be seen by a specialist, as routinely done in Geneva. As recommended,  diagnosis will be made using oral food challenge, basophil activation test, or mast cell activation test; sensitisation defined using skin prick tests results and serum-specific IgE concentration (including allergen component-resolved diagnostics).  Wheezing diseases – parent-reported doctor-diagnosed wheezing episode (bronchiolitis or infant asthma).   For each allergic disease: age at diagnosis, date, duration and severity of episodes/flare, outcome, treatment.
Potential confounding factors post randomisation: breastfeeding (age at cessation); formula (type); solid feeding (age at introduction of different foods); smoking exposure; childcare attendance (index & siblings); travel; pet exposure; vitamin D supplementation; probiotic intake; paracetamol/ibuprofen use; antibiotics; other vaccinations (which and when).

Table 4: Summary of clinical data that will be collected.

\* Collection of participants' date of birth is needed to determine the season of birth (see table 4 above), as well as the time range for the visits (see section 9.3).

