### 4.3 Secondary Objectives

#### Clinical objectives

#### Stage A

**AIM1:** Determine whether early MMR vaccination (6 months of age) reduces the number and severity of **infections** with unrelated pathogens between 6 months and 9 months of age.

*Hypothesis:* Children receiving early MMR are less likely to develop infections between 6 months and 9 months of age because of trained immunity induced by the live-attenuated MMR vaccine, compared to controls who received a non-live vaccine (DTP) as their last vaccination. The difference between the two groups is most likely to be seen for respiratory infections, but might as well be observed for other infections, justify them to be included as secondary objectives.

**AIM2:** Determine whether early MMR vaccination (6 months of age) reduces the risk and severity of **atopic and allergic diseases** between 6 months and 9 months of age.

*Hypothesis:* MMR acts as an early-life stimulus and prevents allergy by skewing the developing immune system toward a Th1 response, with corresponding down-regulation of Th2 responses.

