## 5. STUDY OUTCOMES

### 5.1 Primary Outcome

#### Stage A

**AIM1:** Number of parent-reported respiratory infections between 6 months and 9 months of age.

*Justification:* As shown in previous studies on the non-specific effect of vaccines, the difference between the two groups is most likely to be seen for respiratory infections, justifying it to be the primary outcome measure. This outcome measure is also clinically relevant given the high burden of disease attributable to respiratory infections in infants.

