### 5.2 Secondary Outcomes

#### Clinical outcomes

##### Stages A and B

**AIM1&3: Infections:** Additional measures of infection, with measurement of the following events: any infection, otitis, upper/lower respiratory tract infection, gastroenteritis, urinary tract infection, osteoarticular infection, and trauma/accident (the latter being used as 'negative control' events), including (i) time to first event, (ii) prevalence, (iii) incidence, (iv) days free of event, (v) severity (duration, antibiotic use, hospitalisation, and outcome) of each event, measured between 6 months and 24 months of life.

*Justification:* The trained immunity induced by MMR vaccination will not only reduce the risk of infection overall, but also decrease their severity

**AIMS2&4: Allergic and atopic diseases:** Eczema, food allergy, and wheezing diseases measured as (i) time to first event/flare, (ii) prevalence, (iii) incidence of event/flaring, (iv) days free of event/flare, (v) severity (scores (see below), treatment, hospitalisation, impact on growth and quality of life) of each event/flare, measured between 6 months and 24 months of life.

*Justification:* The trained immunity induced by MMR vaccination will reduce the risk of developing allergic disease and decrease their severity

**AIM5: Influence of interventions, children, maternal and environmental factors on study outcomes:** Factorial and multivariate analyses will assess the impact of interventions (early MMR, non-concomitant MMR), host factors (e.g. sex, ethnicity), exposure (e.g. day-care, siblings, pets, smoking), underlying immunity (e.g. previous infections), and familial history (e.g. allergy) on clinical outcomes defined above.

*Justification:* Both interventions are expected to have non-specific effects but it is unclear to whether they are synergistic. The other factors listed above are known to possibly influence the non-specific effect of vaccines. Understanding to what extent they influence the non-specific effect of MMR would help identifying subgroup that would benefit the most from a modified vaccination schedule.

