## 9.2.2 Assessment of secondary outcomes

### Clinical outcomes

#### Stages A and B

#### AIM1&3: Infections

*Outcome measure:* Additional measures of infection, with measurement of the following events: any infection, otitis, upper respiratory tract infection, lower respiratory tract infection, gastroenteritis, urinary tract infection, osteoarticular infection, and trauma/accident (the latter being used as control event), including:

- (i) **Time to first event** – Calculated as:  
For participants who have an event:  
*Date of event onset - date of randomisation*  
For participants who did not have an event:  
*Earliest censoring date - date of randomisation*
- (ii) **Prevalence** - Calculated as:  
*number of participants who have an event / total number of participants*
- (iii) **Incidence** - Calculated as:  
*number of events / total time of follow-up*
- (iv) **Days free of event** - Calculated as:  
*number of days free of event / total days of follow-up of participants*
- (v) **Severity of event** – measured as:
  1. **Duration** – Per event, calculated as: *date of recovery - date of onset*
  2. **Antibiotic use** - Per event, including: *yes/no, antibiotic name, dose, route, duration*
  3. **Hospitalisation** - Per event, including: *yes/no, ward/critical care, duration, treatment received*
  4. **Outcome** - Per event, including: *uneventful/complication/sequel/death*

of each category of event, measured between 6 months and 24 months of life, using fortnightly REDCap questionnaires, with validation of data by confirmation with treating paediatrician and medical records.

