#### AIMS2&4: Allergic and atopic diseases

*Outcome measure:* Occurrence and flare of eczema, food allergy, and wheezing diseases (defined as mentioned in table 4) measured as:

- (i) **Time to first event** – Calculated as:  
For participants who have a flare:  
*Date of event onset - date of randomisation*  
For participants who did not have a flare:  
*Earliest censoring date - date of randomisation*
- (ii) **Prevalence** - Calculated as:  
*number of participants who have a flare / total number of participants*
- (iii) **Incidence** - Calculated as:  
*number of flares / total time of follow-up*

- (iv) **Days free of flare** - Calculated as:  
*number of days free of flare / total days of follow-up of participants*
- (v) **Severity of flare** – measured using:
1. **Scores** – e.g. *POEM* and *SCORAD* (see table 4)
  2. **Treatment use** - Per flare, including: *yes/no, treatment name, dose, route, duration*
  3. **Hospitalisation** - Per flare, including: *yes/no, ward/critical care, duration*
  4. **Outcome** - Per flare, including: *uneventful/complication/sequel/death*
  5. **Impact on growth** – Calculated using: *evolution of biometric percentile*
  6. **Impact on quality of life** – Calculated using scores, e.g. items from *POEM* and *SCORAD*

of each event/flare, measured between 6 months and 24 months of life, using fortnightly REDCap questionnaires, with validation of data by confirmation with treating paediatrician and medical records.

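### Bronchiolitis meets both the infection definition and the wheezing-disease definition under allergic outcomes, so a fall in wheeze could reflect fewer infections and would not be independent evidence on allergy

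*Protocol*

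**What the plan says.** Table 4 (section 9.2) sets out the clinical data. Its infection block covers "upper/lower respiratory tract infection (including croup, pharyngitis, otitis media, bronchiolitis, bronchitis, pneumonia", among other infections. Its allergic block covers "presence of eczema, food allergy, wheezing disease", and wheezing diseases are there defined as a "parent-reported doctor-diagnosed wheezing episode (bronchiolitis or infant asthma". Bronchiolitis is thus one item in a list of infections and one of the two diagnoses that make up wheezing disease.

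The outcome sections put both blocks to use:

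- Section 5.1 makes the primary outcome the "Number of parent-reported respiratory infections between 6 months and 9 months of age".
- Section 9.2.2 lists the AIM1 and AIM3 infection events as "any infection, otitis, upper respiratory tract infection, lower respiratory tract infection, gastroenteritis, urinary tract infection, osteoarticular infection, and trauma/accident".
- Section 9.2.2 defines the AIM2 and AIM4 outcome as "Occurrence and flare of eczema, food allergy, and wheezing diseases (defined as mentioned in table 4) measured as". Section 5.2 names the same three diseases under its heading for allergic and atopic diseases.

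No section assigns a bronchiolitis episode to one family only, or plans a wheeze analysis that leaves it out.

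**The concern.** The protocol asks two questions: whether the modified schedule reduces infections with unrelated pathogens (AIM1, AIM3), and whether it reduces atopic and allergic disease (AIM2, AIM4). For the second, section 4.3 offers the hypothesis that "MMR acts as an early-life stimulus and prevents allergy by skewing the developing immune system toward a Th1 response". An outcome meant to answer the allergy question should not move merely because the infection question has a positive answer.

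As defined, wheezing can do so. The primary hypothesis predicts fewer respiratory infections after early MMR. If that is true and extends to bronchiolitis, wheezing disease falls too, even if infant asthma does not change. The overlap runs through all the parallel measures in section 9.2.2: time to first event, prevalence, incidence, days free of events and hospitalisation. At stake is how the wheezing result under AIM2 and AIM4 is read. It could be taken as support for an effect on allergy, and as separate from the infection result, when some of the same episodes produced both.

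**Working it through.** **1. Does one episode qualify twice?** Take a doctor-diagnosed bronchiolitis at 7 months, reported by the parent.

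| Outcome | Where defined | Counted? |
|---|---|---|
| Respiratory infection, 6 to 9 months (primary) | 5.1, 9.2.1, Table 4 infection block | Yes |
| Lower respiratory tract infection, any infection (AIM1) | 9.2.2, Table 4 infection block | Yes |
| Wheezing disease (AIM2) | 9.2.2, Table 4 allergic block | Yes |
| Eczema, food allergy (AIM2) | Table 4, own diagnostic criteria | No |

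Placing bronchiolitis in the lower tract is the ordinary reading, since Table 4 gives upper and lower tract infections as one list. The same double counting applies to AIM3 and AIM4 between 13 and 24 months, without the primary outcome.

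**2. The plan's own figure.** Inputs from section 11.2: control rate 0.29 episodes per month, SD 0.32, 30% reduction, 80% power, two-sided 0.05, 85% completion.

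- Difference: 0.30 × 0.29 = 0.087 per month.
- Per group: 2 × (1.96 + 0.84)² × 0.32² / 0.087², which rounds up to 213.
- With 15% loss: 213 / 0.85, rounded up to 251 per group, 502 in total against the stated 500.

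The sample size reproduces. It depends on the primary outcome only, so changing how wheeze is classified leaves it as it is.

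**3. How far could wheeze move with no effect on allergy?** Let s be the share of control-group wheezing episodes that are bronchiolitis. The protocol gives no value, so s is assumed. Assume also a 30% fall in bronchiolitis, borrowed from the design effect for all respiratory infections, and no effect on other wheeze. Then

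rate ratio for wheeze = (1 − s) + 0.70 × s = 1 − 0.30 × s.

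| s (assumed) | Wheeze rate ratio |
|---|---|
| 25% | 0.925 |
| 50% | 0.85 |
| 75% | 0.775 |
| 90% | 0.73 |
| 100% | 0.70 |

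With bronchiolitis left out of the wheeze outcome, the expected ratio under the same assumptions is 1.00.

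**4. Would a shift of that size be noticed?** This needs one more assumption, the control prevalence of wheeze. Take 212 evaluable children per group (0.85 × 250 = 212.5) and apply the ratios above to a prevalence of 10% to 40%. The chance of two-sided p<0.05 favouring early MMR is about 8% to 25% at s = 50%, and about 13% to 49% at s = 75%. It would be 2.5% in that direction if nothing moved. Section 11.4 sets the 0.05 criterion for the primary outcome, so these figures show scale and are not an error rate of the plan.

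**The case against.** The case on the other side has real weight.

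- **Mislabelling is not certain.** A reader might infer that an infection effect will be reported as an effect on allergy. The documents do not support that. It would need a real effect of MMR on bronchiolitis, and authors who take wheeze alone as allergy. Wheezing is reported by name, and the synopsis lists it beside eczema and food allergy without calling the three allergic. What stands is that Table 4 and the AIM2 and AIM4 headings do call it allergic, which invites that reading.
- **AIM2 and AIM4 are not compromised as a whole.** A reader might infer this too. Eczema and food allergy have their own definitions in Table 4, and no allergy composite is planned. A fall in wheeze with no change in the other two would itself be informative.
- **The mechanisms are not cleanly separate.** Section 5.2 attributes the allergy effect to trained immunity, as it does for infection. The point therefore rests on the shared episodes, not on distinct biology.
- **The grouping may be deliberate.** Table 4 cites a review of preschool wheeze at this definition. Whether it supports pooling the two diagnoses cannot be checked here. Even if it does, the pooled outcome remains unable to separate allergy from infection.
- **The statistical analysis plan could handle it.** Section 11.4 defers full analysis details there. A missing allocation rule would be no finding, but the definition is fixed in the protocol, and an analysis plan that follows it inherits the overlap.
- **Removing bronchiolitis outright has its own risk.** The outcome would then hang on a bronchiolitis-or-asthma label in a parent-reported diagnosis, in an open-label trial without placebo. This stands and shapes the fix.

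**Conclusion.** The point holds as a matter of definition: bronchiolitis counts as a respiratory infection and as an allergic wheezing disease, and nothing in the protocol separates the two uses. If MMR lowers bronchiolitis, the wheezing outcome could fall with no effect on allergy, and it would not corroborate the infection result independently.

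The reach is limited to one secondary component. Eczema, food allergy, the primary analysis and N=500 are untouched. The size is illustrative: 0.85 to 0.73 rests on an assumed bronchiolitis share of 50% to 90%, an assumed 30% fall in bronchiolitis and no effect on other wheeze. With a smaller share or a smaller effect the shift shrinks in proportion, and with no effect on bronchiolitis there is none.

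**What to change.** Before the analysis, state in the protocol or the statistical analysis plan that:

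1. the allergy interpretation of wheeze under AIM2 and AIM4 rests on doctor-diagnosed wheeze not coded as bronchiolitis;
2. any wheeze including bronchiolitis is reported alongside it, split by diagnosis, with a statement that it is not evidence on allergy by itself;
3. bronchiolitis stays in the infection outcomes, including the primary, as now.

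No new data are needed, because section 9.2 already plans to record the diagnosis for each infectious and allergic episode. The allergy-specific wheeze component will have fewer events and a wider confidence interval. Some episodes will also be misclassified between bronchiolitis and infant asthma at this age, which is why the pooled result is kept beside it and not dropped.
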